The currently recommended antiplatelet treatment regimen for patients affected by acute coronary syndromes (ACS) and those undergoing percutaneous coronary intervention (PCI) consists in the combination of aspirin and a $P2Y_{12}$ receptor inhibitor [1-3]. Currently, three $P2Y_{12}$ receptor inhibitors are available for clinical use (clopidogrel, prasugrel, and ticagrelor). Among these, clopidogrel remains the most widely used to reduce recurrent ischemic events [1, 4,5,6]. However, several studies have shown that there is a broad variability in platelet-inhibitory response induced by clopidogrel, which in turn is associated with worse outcomes [7]. Variability in clopidogrel response is a multifactorial process [7]. Clopidogrel is a prodrug that requires bioactivation into its active metabolite before targeting the P2Y₁₂ receptor on blood platelets. In vivo bioactivation of the drug is a 2-step process that is closely linked to the cytochrome P450 (CYP) system [8]. The most prominent and best established genetic factor is located within the CYP2C19 gene, as the polymorphically expressed isoenzyme CYP2C19 is involved in both metabolic steps of clopidogrel's active metabolite generation [8,9]. In particular, a single-nucleotide polymorphism located within the CYP2C19 gene is a major determinant of clopidogrel responsiveness [9]. The presence of CYP2C19*2 and CYP2C19*3 LOF allelic variants is associated with a loss of enzyme function and comes along with an attenuated response to clopidogrel leading to higher risk for ischemic events [10]. CYP2C19 *2 allele is the most common LOF variant with allele frequencies of ~15% in Caucasians and Africans, and 29-35% in Asians [11].

More potent P2Y₁₂ receptor inhibitors (prasugrel and ticagrelor) have been developed and are associated with less response variability than clopidogrel and better clinical outcomes in

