patients with ACS [12,13,14,15]. Ticagrelor use has increased significantly because of its more expanded Food and Drug Administration (FDA) indications compared with prasugrel [1,4,5,14,15]. However, despite the evidence for consistent and sustained efficacy and safety of ticagrelor with up to one-year of treatment, many physicians limit treatment duration with ticagrelor to the early phases following an ACS (early weeks or months) rather than one-year mostly due to cost issues and concerns about increased bleeding [14,16]. The PD profiles after discontinuation of ticagrelor indicate faster recovery of platelet-inhibitory effects than clopidogrel [17], suggesting the need for early overlap of treatment among ticagrelor-treated patients in case of switching antiplatelet therapy. In the SWAP-2 (Switching AntiPlatelet-2) study in which patients were switched from ticagrelor to prasugrel, a loading-dose (LD) appeared to be essential to mitigate a rebound in platelet reactivity due to a drug-interaction after switching [18]. This study also hypothesized that this potential drug-drug interaction could have been attributed to the presence of ticagrelor or its metabolite still on the P2Y₁₂ receptor when prasugrel was administered after 12 hours from the last maintenance dose (MD) of ticagrelor. This also suggested that switching should occur after a later time frame (e.g. 24 hours) to enable more time for the receptor to be unbounded by ticagrelor or its metabolite to allow a better switching approach [18]. However, to date, the PD effect of switching from ticagrelor to clopidogrel, and how this may be affected by administering a LD prior to initiating a standard MD regimen, as well as how this may be affected by timing of administration from last MD, has not been explored. Moreover, if such PD response profiles can be affected by CYP2C19 LOF genetic status also remains unknown.

Study aim

The aim of this investigation is to evaluate the PD effects of switching from ticagrelor to clopidogrel with and without a LD., and to evaluate how this might be affected by CYP2C19 LOF genetic status.

Study Population

Patients with known coronary artery disease (CAD) on maintenance aspirin (<100mg qd) and clopidogrel therapy (75mg qd) as a part of their standard-of-care will be screened for this study. Details of inclusion and exclusion criteria are described below:

Inclusion Criteria

- 1) Patients with angiographically documented CAD

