- On therapy with aspirin(<100mg/day) and clopidogrel (75mg/day) for at least 30 days per standard of care
- 3) Age between 18 and 80 years old

Exclusion Criteria

- 1) History of intracranial bleeding
- 2) Known hepatic impairment (based on clinical judgment)
- 3) Active bleeding or propensity to bleed or blood dycrasia
- 4) Platelet count $< 80 \times 10^6 / \text{mL}$
- 5) Hemoglobin <10g/dL
- 6) Hemodynamic instability
- 7) Estimated glomerular filtration rate (eGFR) <30 mL/min
- 8) On treatment with oral anticoagulants
- 9) Patients with sick sinus syndrome (SSS) or II or III degree AV block without pacemaker protection

[figure not shown]
- 10) Drugs interfering CYP3A4 metabolism (to avoid interaction with ticagrelor): ketoconazole, itraconazole, voriconazole, clarithromicin, nefazodone, ritonavir, saquinavir, nelfinavir, indinavir, atazanavir and telithromizycin
- 11) Pregnant females [women of childbearing age must use reliable birth control (i.e. oral contraceptives) while participating in the study].

Research design

Patients meeting inclusion criteria will be enrolled in this prospective, randomized, openlabel study. Baseline labs obtained within the past 180 days will be considered valid for screening purposes. If baseline labs are not available, these will need to be obtained prior to considering a patient eligible for study entry (patients will have 90 days to enter the study). Eligible patients will undergo a 7±2 day run-in phase with ticagrelor after switching from clopidogrel 75mg/day to ticagrelor 180mg LD followed by 90mg bid MD. Ticagrelor dosing in this study is line with FDA recommendations [15]. After this run-in phase, patients will be randomized (1:1:1:1) into one of the four following groups: A) clopidogrel 600 mg LD 24 hours after last MD of ticagrelor, followed by 75mg daily MD; B) clopidogrel 600 mg LD 12 hours after last MD of ticagrelor, followed by 75mg daily MD; C) clopidogrel 75mg daily MD 24 hours after last MD of ticagrelor; D) continue ticagrelor MD 90mg twice daily. The FDA approved dose for clopidogrel is 300 mg loading dose and 75 mg/qd maintenance dose; however standard of care loading dose is 600 mg which is in line with practice guidelines [1-5].

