Blood sampling: Peripheral venous blood samples (20 mL) will be drawn through a short venous catheter inserted into a forearm vein and collected in citrate, EDTA, and serum tubes as appropriate for assessments. The first 2-4 mL of blood will be discarded to avoid spontaneous

platelet activation. Blood sampling for PD will be performed at the following time points: prior to run-in baseline visit (24 hours after last clopidogrel dose in order to assess trough levels of platelet reactivity), after run-in (12 hours after last ticagrelor maintenance dose of run-in period), 24 hours after washout (groups A and C only), and 2, 24, 48, 72 hours and 10±3 days after randomization. For patients randomized to groups A and C, both requiring 24 hours washout from last MD, they will take their morning MD of ticagrelor after blood sample collection for their post-run-in phase and return the following morning to receive the randomized treatment (these groups will have a total of 8 blood sampling time points). Patients randomized to groups B and D will initiate their randomized treatment the same morning of the post-run-in phase visit (these groups will have a total of 7 blood sampling time points). CYP2C19 genetic status will be evaluated at baseline visit. PD assessment will include VerifyNow point-of-care testing (VN-P2Y₁₂), light-transmittance aggregometry (LTA) and whole blood vasodilator-stimulated phosphoprotein (VASP) as described below. Time points will have a $\pm 10\%$ window. Results of genetic testing will not be used for clinical decision makings on choice of antiplatelet treatment regimen to be used at the end of the study. This is because we are studying patients in stable clinical conditions who have already on maintenance clopidogrel therapy without experiencing ischemic events, which are more likely to occur in the earlier phases of treatment in the setting of PCI [10]. Moreover, routine genetic testing and modification of treatment based on results of genetic testing is a class III recommendation in practice guidelines [1,2]. An illustration of the study design is provided below. A study table summarizing protocol procedures is provided as an appendix.

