antibodies by flow cytometry with the Platelet VASP-FCM kit (Biocytex Inc., Marseille, France) as previously described [19]. PGE1 increases VASP-P levels by stimulation of adenylate cyclase. Binding of ADP to P2Y₁₂ leads to Gi-coupled inhibition of adenylate cyclase. Therefore, the addition of ADP to PGE1-stimulated platelets reduces PGE1-induced VASP-P levels. If P2Y₁₂ receptors are successfully inhibited by inhibitors, addition of ADP will not reduce the PGE1-stimulated VASP-P levels. The platelet reactivity ratio (PRI) will be calculated after measuring VASP-P levels after stimulation with PGE1 (MFI PGE1) and also PGE1 + ADP (MFI PGE1 + ADP). The P2Y₁₂ reactivity ratio = ([MFI PGE1] – [MFI PGE1 + ADP]/[MFI PGE1]) x 100%.

4) CYP 2C19 Genetic testing: CYP2C19 genetic status will be performed with the Spartan RX point-of-care rapid genotyping device. Spartan RX (Spartan Bioscience Inc., Ontario, Canada) is a point-of-care determining the CYP2C19 (*1,*2,*3,*17) allele status within 1 hour [20]. This test consisted of four separate steps intended to be done in less than 8 minutes: acquisition of a buccal swab; insertion of the swab into the cartridge; insertion of the reaction solution into the device; and analysis of CYP2C19 genotype triggered by a button on the device. In particular, this point-of-care assay enables assessment of the following alleles: *1,*2,*3 and *17. The most common LOF alleles are *2 and *3. Therefore, carriers of *2 or *3 LOF carrier status can be homozygotes (*2/*2, *3/*3 or *2/*3) or heterozygotes (*1/*2, *1/*3, *2/*17, *3/*17). Non-carriers of LOF alleles include the following: *1/*1, *1/*17 or *17/*17.

Definitions of high on treatment platelet reactivity

High on-treatment platelet reactivity (HPR) will be defined according to updated expert consensus as following: PRU higher than 208 or 235, MPA-ADP (5 μ M) >46%, MPA-ADP (20 μ M) >59% and VASP-PRI >50% [21,22].

Study endpoints and sample size calculation

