The primary endpoint is the comparison of PRU assessed by VN- P2Y₁₂ at 48 hours after switching from ticagrelor 90 mg bid to clopidogrel 600 mg LD given 24 hours after last ticagrelor MD (group A) vs. clopidogrel 75 mg MD given 24 hours after last ticagrelor MD (group C). We hypothesize that switching from ticagrelor to clopidogrel with a loading dose will have less increase in platelet reactivity than that without loading dose and the sample size was determined based on the objective of establishing superiority of this approach. Superiority will be assessed using a 95% confidence interval (CI) of the difference in mean PRU between these two groups. Under the assumption of a mean difference of 60 PRU between groups and a common standard deviation of 50 PRU, a sample size of 16 per group allows for the 95% CI with a 95% power and alpha=0.05. Considering 4 arms of treatment and a possible invalid data in 20-25% of patients due to technical issues or drop-outs, we will randomize up to a total of 80 patients to ensure complete data. We anticipate screening 100 patients to identify these 80 patients to be randomized. Secondary endpoints include comparison of PRU (other than primary endpoint) assessed by VN-P2Y₁₂, 5 and 20 µM ADP aggregation assessed by LTA and VASP-PRI in all four groups at each time points; rates of HPR according to each platelet function assay

(VN-P2Y₁₂, LTA, and VASP-PRI) in all four groups at each time point; impact of CYP2C19 LOF genetic status on PD parameters.

Statistical analysis plan

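### CYP2C19 LOF status is known before randomisation and its effect is part of the aim, but neither the allocation nor the ANCOVA uses it: avoidable loss of precision, not bias

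*Combined protocol and SAP*

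**What the plan says.** - **Prognostic role.** Background and Significance says that "a single-nucleotide polymorphism located within the CYP2C19 gene is a major determinant of clopidogrel responsiveness". It gives no effect size in PRU. For the *2 allele it gives "allele frequencies of ~15% in Caucasians and Africans, and 29-35% in Asians".
- **Aim and endpoint.** The Study aim includes the intention "to evaluate how this might be affected by CYP2C19 LOF genetic status". Study endpoints and sample size calculation lists "impact of CYP2C19 LOF genetic status on PD parameters" as a secondary endpoint.
- **Timing.** Under Blood sampling, "CYP2C19 genetic status will be evaluated at baseline visit". Table S1 places the test at V1 and randomisation at V2, after the 7±2 day run-in. The assay description says the device gives "allele status within 1 hour".
- **Allocation.** Research design says that "patients will be randomized (1:1:1:1) into one of the four following groups". The text and Table S1 describe no stratification, blocking or minimisation.
- **Analysis.** The Statistical analysis plan specifies ANCOVA for all between-group comparisons, with the baseline value of platelet reactivity as the covariate. Genotype does not appear in it, and no model is given for the genetic endpoint. The plan does not say which sample is the baseline.

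**The concern.** The trial measures a factor that it regards as strongly prognostic, has the result before allocation, and then uses it in neither the design nor the primary model. With 16 to 20 patients per arm, carrier numbers in A and C can differ by several patients by chance. Without adjustment, that difference stays in the A vs C estimate as error that data already collected could remove.

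The genetic part of the aim also has no stated analysis. About 28% of patients are expected to be carriers, so how their data are combined largely decides whether this part of the aim yields a usable estimate.

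**Working it through.** **Inputs from the documents.** A vs C difference 60 PRU and SD 50 PRU ("Under the assumption of a mean difference of 60 PRU between groups and a common standard deviation of 50 PRU"); 16 per group for 95% power at alpha 0.05; 20-25% invalid data; up to 80 randomised (20 per arm); two-tailed 0.05; allele frequency about 15%.

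**Assumptions.** Hardy-Weinberg proportions, *2 allele only, and a carrier effect L of 30 to 60 PRU. The documents give no value for L.

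**1. The plan's own sample size.** n = 2·SD²·(z_alpha + z_beta)²/difference².
- One-sided 0.05: 2·2500·(1.645 + 1.645)²/3600 = 15.03, so 16. The t-test power at 16 is 95.3%, which reproduces the stated figure.
- Two-sided 0.05, as the Statistical analysis plan requires: 2·2500·(1.960 + 1.645)²/3600 = 18.05, so 19. The t-test power at 16 is 90.7%.
- Total: 4·16/(1 − 0.20) = 80, as stated.

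The power comparisons below therefore start from 90.7%.

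**2. Carriers per arm.** p = 1 − 0.85² = 0.2775. Expected: 20·0.2775 = 5.6, or 16·0.2775 = 4.4. In a population with 29-35% allele frequency, p would be about 50-58%.

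**3. Imbalance between A and C (two independent binomials).** P(difference of 4 or more, either direction) = 16% at n=16 and 21% at n=20.

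**4. Effect on the unadjusted A vs C difference.** Shift = (4/n)·L.
- n=16: 0.25·30 = 7.5 to 0.25·60 = 15 PRU. SE = 50·√(2/16) = 17.7 PRU.
- n=20: 0.20·30 = 6 to 0.20·60 = 12 PRU. SE = 50·√(2/20) = 15.8 PRU.

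**5. Type I error.** A simulated unadjusted t-test under unstratified allocation rejected in 5.0-5.1% of null trials for L = 30 and 60.

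**6. Gain from adjustment.** Variance share of genotype = p(1 − p)L²/SD² = 0.2005·900/2500 = 7% to 0.2005·3600/2500 = 29%. Residual SD = 50·√(1 − share) = 48.2 to 42.2 PRU. Two-sided t-test power at 16 per arm, with the covariate-only row averaged over chance imbalance:

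| Approach | L = 30 | L = 60 |
|---|---|---|
| No LOF adjustment | 90.7% | 90.7% |
| LOF covariate, no stratification | 91.7% | 96.8% |
| LOF covariate plus stratification | 92.6% | 97.3% |

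Stratification adds 0.9 and 0.5 percentage points to what the covariate gives.

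**7. What the genetic aim can detect (80% power, 16 per arm, factor 2.8, SD 50).**
- LOF effect pooled over A, B and C (13.3 carriers, 34.7 non-carriers): 2.8·50·√(1/13.3 + 1/34.7) = 45 PRU.
- LOF effect in one arm (4.44 and 11.56): 2.8·50·√(1/4.44 + 1/11.56) = 78 PRU.
- Treatment-by-LOF interaction, A vs C: 2.8·50·√(2/4.44 + 2/11.56) = 111 PRU.

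**8. Sparse carrier cells in the clopidogrel arms.** P(one arm has 2 or fewer) = 0.055 at n=20 and 0.137 at n=16. For at least one of A, B and C: 1 − (1 − 0.055)³ = 16% and 1 − (1 − 0.137)³ = 36%. For 1 or fewer: 4% and 11%.

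**The case against.** Unstratified allocation is a defensible choice in an 80-patient pharmacodynamic study. Four counter-arguments stand, and each limits the point.

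- **Bias.** A reader might infer that imbalance invalidates the A vs C comparison. It does not. Genotype variance is already inside the overall SD of 50 and therefore inside the confidence interval, and type I error stays at 5%. Even the larger shifts in step 4 are below one standard error.
- **Which baseline.** A reader might infer that the ANCOVA baseline is taken on ticagrelor and so says nothing about clopidogrel response. The documents do not establish this. Blood sampling uses the term baseline visit for V1, 24 hours after the last clopidogrel dose, while Table S1 labels the V2 and V3 samples as baseline PD. If V1 is meant, the covariate already carries part of the genotype effect, and the gains in step 6 are upper figures.
- **Almost no carriers.** A reader might infer that some arms will be left nearly without carriers. That is a minority outcome (step 8). Group D stays on ticagrelor and does not belong in the count. Stratification also creates no extra carriers: about 22 of 80 are expected either way.
- **Subgroup tests.** Nothing in the documents plans tests within each arm by genotype. The genetic analysis is simply unspecified.

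The statement under Blood sampling that genetic results will not guide treatment concerns the regimen at the end of the study. It does not rule out stratification or adjustment.

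What these arguments do not answer is that a prognostic factor already collected is left out of the primary model at almost no saving.

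**Conclusion.** The point holds as one of efficiency and of an incomplete analysis specification. Nearly all the recoverable precision comes from the missing covariate and very little from the missing stratification. On a 30-60 PRU carrier effect, power at 16 per arm rises from 90.7% to about 92-97% with LOF status in the model; the gain is smaller if the ANCOVA baseline is the V1 sample.

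For the genetic aim, a pooled model can detect about 45 PRU against 78 PRU within one arm. The A vs C interaction, at about 111 PRU, is beyond this trial whatever the allocation method. The sizes rest on 27.75% carriers and on a carrier effect that the documents do not supply.

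**What to change.** 1. Prespecify LOF carrier status (carrier or non-carrier) as a covariate in the A vs C ANCOVA, alongside baseline platelet reactivity. State which sample is the baseline. This also covers patients already randomised, provided it is fixed before analysis.
2. Estimate the LOF effect in one model pooled over A, B and C. Include a treatment-by-LOF term, report it with a 95% CI, and label it exploratory.
3. Optionally, for patients not yet randomised, use permuted blocks within two strata, carrier and non-carrier. This adds under 1 percentage point of power but guards against arms with very few carriers.

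Items 1 and 2 cost a few lines in the Statistical analysis plan and no new procedure, visit or patient. Item 3 needs the genotype on file before V2 and may leave some blocks incomplete, mainly in the carrier stratum of about 22 patients.

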 $P2Y_{12}$ receptor inhibitors. The assay is based upon the ability of activated platelets to bind fibrinogen. Fibrinogen-coated microparticles aggregate in proportion to the number of GP IIb/IIIa receptors expressed. Microbead aggregation is more rapid and reproducible if platelets are activated; therefore the reagents are incorporated into the assay channel to induce platelet activation without fibrin formation. Light transmittance increases as activated platelets bind and aggregate fibrinogen-coated beads. The instrument measures this change in optical signal and reports results in $P2Y_{12}$ Reaction Units (PRU).

- 2) Light transmittance aggregometry (LTA): Platelet aggregation will be measured using LTA according to standard protocols. Blood will be collected in citrated (3.8%) tubes. LTA will be assessed using platelet rich plasma (PRP) by the turbidimetric method in a 2-channel aggregometer (Chrono-Log 490 Model, Chrono-Log Corp., Havertown) as previously described [19]. Platelet agonists will include 5 and 20 μM ADP. PRP will be obtained as a supernatant after centrifugation of citrated blood at 1000 rpm for 10 minutes. The isolated PRP will be kept at 37° C before use. Platelet poor plasma (PPP) will be obtained by a second centrifugation of the blood fraction at 2800 rpm for 10 minutes. Light transmission will be adjusted to 0% with the PRP and to 100% for the PPP for each measurement. Curves will be recorded for 6 minutes and platelet aggregation will be determined as the maximal percent change (MPA) in light transmittance from baseline using PPP as a reference.
- *3) Whole blood vasodilator-stimulated phosphoprotein (VASP):* VASP phosphorylation (VASP-P) is a marker of P2Y₁₂ receptor reactivity, which is the target for ticagrelor. VASP will be assessed according to standard protocol using labeled monoclonal

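### The VASP-PRI formula lacks a bracket around the difference: a minor correction that matters only for the VASP secondary endpoints, and only if the line is coded as printed

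*Combined protocol and SAP*

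**What the plan says.** Under Description of laboratory assays, item 3 (VASP), the protocol introduces the index: "The platelet reactivity ratio (PRI) will be calculated after measuring VASP-P levels after stimulation with PGE1 (MFI PGE1) and also PGE1 + ADP". The formula line follows under the name P2Y12 reactivity ratio. After the opening round and square brackets it reads "MFI PGE1] – [MFI PGE1 + ADP]/[MFI PGE1]) x 100", with a percent sign. The division stands in its second half, "MFI PGE1 + ADP]/[MFI PGE1]) x 100". The only round brackets enclose the whole expression before the multiplication by 100; none encloses the difference.

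The same paragraph describes how the assay behaves. When the P2Y12 receptors are successfully inhibited, "addition of ADP will not reduce the PGE1-stimulated VASP-P levels". The next section, Definitions of high on treatment platelet reactivity, sets HPR at a VASP-PRI above 50%.

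The index is used in Study endpoints and sample size calculation. The secondary endpoints include "aggregation assessed by LTA and VASP-PRI in all four groups at each time points", and then "rates of HPR according to each platelet function assay", with VASP-PRI named among the assays. The effect of CYP2C19 loss-of-function status on the pharmacodynamic parameters is also secondary. The Statistical analysis plan section adds no derivation rule for PRI, and the formula appears nowhere else.

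**The concern.** By ordinary operator precedence, division comes before subtraction, so only the second reading is divided by the PGE1 reading. The result is a fluorescence value minus a unitless ratio, which is not a ratio at all. It conflicts with three things the protocol itself says: that the index is a ratio expressed as a percentage, that ADP has no effect when inhibition is complete (so the index should be zero), and that 50% separates high from acceptable reactivity.

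This line is the only written definition of a named secondary endpoint and of one of the HPR classifications. An analyst who coded from the protocol alone would get values that reflect mainly the strength of the PGE1 signal, and the 50% cut-off would no longer separate patients.

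**Working it through.** **Inputs.** M = MFI PGE1 and A = MFI PGE1 + ADP (VASP assay description). Cut-off: above 50% (HPR definitions). The documents give no MFI values and no worked PRI, so there is no plan figure to reproduce; the values of M below are assumptions. I take 0 <= A <= M, since the protocol says ADP lowers the PGE1-stimulated signal or, at full inhibition, leaves it unchanged. I treat the two names (PRI and P2Y12 reactivity ratio) as the same index.

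**Formulas.**
- As printed: (M - A/M) x 100
- With the difference bracketed: ((M - A)/M) x 100 = (1 - A/M) x 100

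**1. Size over an assumed range, at A/M = 0.5.**

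| M | A | As printed | Bracketed |
|---|---|---|---|
| 5 | 2.5 | (5 - 0.5) x 100 = 450% | 50% |
| 10 | 5 | (10 - 0.5) x 100 = 950% | 50% |
| 20 | 10 | (20 - 0.5) x 100 = 1950% | 50% |
| 50 | 25 | (50 - 0.5) x 100 = 4950% | 50% |
| 100 | 50 | (100 - 0.5) x 100 = 9950% | 50% |

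**2. Full inhibition.** Put A = M. Printed: (M - 1) x 100, for example (20 - 1) x 100 = 1900% at M = 20. Bracketed: 0%, as the protocol's description requires.

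**3. Scale.** Double both readings, from M = 20, A = 10 to M = 40, A = 20. Printed: 1950% becomes (40 - 0.5) x 100 = 3950%. Bracketed: 50% both times.

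**4. The cut-off.** The printed value exceeds 50% when M - A/M > 0.5. Since A/M is at most 1, M > 1.5 is enough, whatever the degree of inhibition. This step needs no assumed MFI beyond that threshold.

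**5. Form of the error.** Printed minus bracketed = (M - A/M) x 100 - (1 - A/M) x 100 = (M - 1) x 100. This is not a constant: it varies with each sample's PGE1 signal. On the printed scale, a one-unit change in M at fixed A/M moves the result by 100 percentage points, as much as going from no inhibition of any kind (A/M = 0) to complete inhibition (A/M = 1). Literal use would therefore distort group comparisons as well as the HPR classification.

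**The case against.** The intended calculation can be recovered from the paragraph itself. A ratio, expressed as a percentage, equal to zero at full inhibition and read against a 50% cut-off, fits only the bracketed form. The protocol also ties the assay to an outside standard: "VASP will be assessed according to standard protocol using labeled monoclonal" antibodies, with a named commercial kit and a cited reference. A laboratory following these may well compute the index correctly whatever this line says. Literal use would also be hard to miss, since it would return values far above 100% even in fully inhibited patients on ticagrelor. All of this stands, and it is why the point is minor.

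A bracket or stacked fraction lost in reading the PDF cannot be wholly excluded, but the slash, the square brackets and the outer round brackets all survive on one line, so it is unlikely.

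A reader might infer that the trial's VASP results are wrong, or that essentially every patient would be reported as HPR. The documents do not support that: nothing in them shows that the printed form was or would be used. A reader might also take values in the thousands of percent as a fact. That too goes beyond the documents. A result of at least 1000% at every A/M from 0 to 1 needs M of 11 or more, since (11 - 1) x 100 = 1000; at M = 5 to 10 the values in this calculation are in the hundreds.

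What the objection does not remove is that the only written definition of the endpoint is incorrect, and that a correct laboratory procedure would then disagree with the protocol.

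**Conclusion.** The formula is wrong as written, and the inner bracket is needed. That conclusion follows from the protocol's own description and cut-off and rests on no outside source. Failure of the 50% cut-off under literal use requires only M above 1.5 with A no greater than M. The range of 450% to 9950% against 50% is illustrative, because it rests on assumed readings.

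The reach is narrow: VASP-PRI as a continuous value, the VASP-based HPR rates, and the VASP part of the CYP2C19 analysis, and these only if the line is coded literally. The primary endpoint, PRU at 48 hours in group A versus group C, is reported by the VerifyNow instrument and is untouched, as are the sample size and the aggregometry endpoints. It is most probably a typographical slip. Severity: minor.

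**What to change.** Restate the formula as PRI = (([MFI PGE1] - [MFI PGE1 + ADP]) / [MFI PGE1]) x 100%, and use one name for the index throughout. Confirm that the spreadsheet or software that derives PRI uses this form. A quick test is enough: equal readings must return 0%, and an ADP reading of half the PGE1 reading must return 50%.

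The cost is one pair of brackets and one check of the calculation. The design, the sample size and the analysis methods do not change.

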Continuous variables will be expressed as a mean \pm SD when are normally distributed or median [IQR] when are not normally distributed. Categorical variables will be expressed as frequencies and percentages. The Kolmogorov-Smirnov test will be used to examine data distribution normality. Comparisons between categorical variables will be performed using twotailed Fisher's exact test or the Pearson's chi-square test. Student's t test, Mann-Whitney U-test and Wilcoxon test will be used to compare continuous variables when appropriate. A repeated measures analysis of variance (ANOVA) model will be used to evaluate intra-group comparisons and the overall difference between groups. An analysis of covariance (ANCOVA) method with a general linear model, using the baseline value of platelet reactivity as a covariate, will be used to evaluate all between-groups comparisons. Missing data will not be imputed. A 2-tailed p value of < 0.05 is considered to indicate a statistically significant difference for all the analyses performed. Statistical analysis will be performed by our group using SPSS v22.0 software (SPSS Inc. Chicago, IL).

Possible Discomforts and Risk

The study entails blood draws at multiple time points as indicated above. The risks of the blood draw may include faintness, inflammation of the vein, pain, bruising or bleeding at the site of the puncture. There is also a slight risk of infection from the blood draw. In clinical trials, the

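### The stated 95% power at 16 per group matches a one-sided 5% test; under the plan's own two-sided rule it is about 91%, and about 89% at 25% loss

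*Combined protocol and SAP*

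**What the plan says.** The section on study endpoints and sample size calculation defines the primary endpoint: "The primary endpoint is the comparison of PRU assessed by VN- P2Y₁₂ at 48 hours after switching", comparing group A (600 mg clopidogrel loading dose 24 hours after the last ticagrelor dose) with group C (75 mg without a loading dose at the same interval). The stated purpose is superiority: "the sample size was determined based on the objective of establishing superiority of this approach". The decision rule follows: "Superiority will be assessed using a 95% confidence interval (CI) of the difference in mean PRU between these two groups".

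The inputs are given as "Under the assumption of a mean difference of 60 PRU between groups and a common standard deviation of 50 PRU", and the result as "a sample size of 16 per group allows for the 95% CI with a 95% power and alpha=0.05". That sentence does not say whether alpha is one- or two-sided.

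The statistical analysis plan section does: "A 2-tailed p value of < 0.05 is considered to indicate a statistically significant difference for all the analyses performed". It also says that missing data will not be imputed, and that between-group comparisons will use ANCOVA with baseline platelet reactivity as covariate.

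On numbers, the research design section says "patients will be randomized (1:1:1:1) into one of the four following groups", and the sample size section allows for "a possible invalid data in 20-25% of patients due to technical issues or drop-outs, we will randomize up to a total of 80 patients" so that data will be complete.

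**The concern.** A conventional 95% confidence interval for a difference in means and a 2-tailed test at 0.05 are the same decision rule, so the two sections agree that the primary test is two-sided. With a standardised difference of 60/50 = 1.2, however, 16 per group is too few for 95% power under that rule. It looks as though the sample size was computed with a one-sided 5% error rate and the analysis was then specified as two-sided.

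The allowance for loss adds to this. Eighty patients over four arms is 20 per arm, and a 25% loss leaves 15, which is below the plan's own target of 16. Because missing values are not imputed, each loss reduces the analysed number directly.

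What is at stake is the power claimed for the one comparison on which the trial was sized. Anyone interpreting a non-significant A vs C result would take the risk of a false negative, under the planning assumptions, to be 5% when it is about twice that.

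**Working it through.** **Inputs**
- Difference 60 PRU, common SD 50 PRU, so d = 60/50 = 1.2 (sample size section).
- 16 per group, 95% power, alpha 0.05 (sample size section).
- Two-sided rule: 95% CI (sample size section) and 2-tailed p < 0.05 (statistical analysis plan section).
- Up to 80 randomised 1:1:1:1, so 20 per arm; loss 20–25%.

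**Step 1. Reproduce the plan's figure (normal approximation).**
n per group = 2 × (z_alpha + z_power)² / d², with z_power = 1.645 for 95%.
- One-sided 0.05: 2 × (1.645 + 1.645)² / 1.44 = 15.03, rounded up to **16**. This is the plan's number.
- Two-sided 0.05: 2 × (1.960 + 1.645)² / 1.44 = 18.05, rounded up to **19**.

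**Step 2. Power by noncentral t.**
Noncentrality = d × √(n/2), df = 2n − 2. For n = 16: 1.2 × √8 = 3.394 with 30 df.
- One-sided 0.05 (critical value 1.697): power 95.3%.
- Two-sided 0.05 (critical value 2.042): power 90.7%.

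| n per group | Two-sided, t | Two-sided, normal | One-sided, t |
|---|---|---|---|
| 15 | 88.7% | 90.8% | 94.1% |
| 16 | 90.7% | 92.4% | 95.3% |
| 19 | 94.9% | 95.9% | 97.6% |
| 20 | 95.9% | 96.7% | 98.1% |

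Under the two-sided rule neither method gives 95% at 16 per group. Strictly, 95% needs 20 per group by the t distribution (19 gives 94.9%), or 19 by the normal approximation. With 16 per group, the difference detectable with 95% power (two-sided, t) is 65.9 PRU rather than 60.

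**Step 3. Loss.**
- 20% loss: 80 × 0.80 / 4 = 16 per group, power 90.7%.
- 25% loss: 80 × 0.75 / 4 = 15 per group, power 88.7%.
- To keep 16 after 25% loss: 16 / 0.75 = 21.3, so 22 per arm, not 20.
- To keep 20: 20 / 0.80 = 25 per arm (100 in total), or 20 / 0.75 = 26.7, so 27 per arm (108 in total).

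**Step 4. Effect of baseline adjustment.**
The documents give no correlation r between baseline and 48-hour PRU, so r is an assumption here. With residual SD = 50 × √(1 − r²) and one fewer df, two-sided power is:

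| r | n = 16 | n = 15 |
|---|---|---|
| 0 | 90.7% | 88.6% |
| 0.3 | 93.0% | 91.3% |
| 0.4 | 94.7% | 93.3% |
| 0.5 | 96.6% | 95.5% |

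Power reaches 95% at r of about 0.42 with 16 per group and about 0.48 with 15.

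**The case against.** The strongest counter-argument is the planned ANCOVA. The statistical analysis plan section applies it to all between-group comparisons, which includes A vs C, and a moderate baseline correlation would bring two-sided power back to 95% at 16 per group. This shows that the true power of the adjusted analysis might be 95%. It does not support the stated figure: the sample size paragraph does not mention the covariate, does not describe the SD of 50 as a residual SD, and gives no correlation. The claim that 95% needs a one-sided test is therefore a claim about the unadjusted comparison that the paragraph describes.

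A second argument is that the hypothesis is directional, so a one-sided alpha may have been intended. Expecting a direction does not make the test one-sided, and the 2-tailed rule allows no exception. If one-sided was meant, the two sections conflict and still need correcting.

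Third, the shortfall is modest. That is right: power stays at about 89–91% over the stated loss range, or 91–92% by the normal approximation, and by that approximation the type II error at 16 per group is 7.6%, about one and a half times 5% rather than double. At 19 per group the exact power rounds to 95%, so needing all 20 is the strict reading.

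Fourth, the plan does not say in so many words that 16 per arm will remain after 25% loss, and 64 increased by a quarter is also 80, so the loss range may express one allowance on two bases. That reading is possible, but the text describes the percentage as a share of patients with invalid data, and 25% of 80 leaves 60.

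**Conclusion.** The point holds. With a 60 PRU difference, an SD of 50 and the plan's two-sided 5% rule, 16 per group gives 90.7% power for an unadjusted comparison, not 95%. At 25% loss it is 88.7%. The type II error is 9.3–11.3% against the stated 5%. The stated pairing of 16 per group with 95% power comes from a one-sided alpha of 0.05 that the plan does not adopt.

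This is an overstated power, not an inadequate trial. It rests on the plan's own effect size and SD, equal allocation, loss spread evenly over the arms, and no gain from baseline adjustment. Such a gain could close the gap if the correlation were about 0.42 or higher, but nothing in the documents supports a value.

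**What to change.** Restate the sample size paragraph. It should say that alpha is two-sided 0.05; that 16 evaluable per group gives about 91% power for a difference of 60 PRU with SD 50; and that 15 per group, the result of 25% loss from 80 randomised, gives about 89%. It should also say that 80 randomised secures 16 per group only if loss is no more than 20%.

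The plan can also name the baseline-adjusted difference at 48 hours, with its two-sided 95% CI, as the primary analysis. The method is already planned; what is missing is the explicit link to the primary endpoint. If power is then quoted for that analysis, the assumed correlation should be stated with a range, as in the last table of the working.

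The cost is a wording change and a slightly less favourable stated power. No extra patients, visits or treatment changes are needed. Keeping a strict two-sided 95% without relying on the covariate would instead take 100 to 108 randomised patients, which the size of the shortfall does not require.
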